**Inclusion Criteria:**

Patients must meet the following criteria to be eligible for participation in the study:

1. Male or female patient  $\geq$  18 years of age.
2. For Dose Escalation Phase Cohorts (Phase 1):
  - a. Have histologically- or cytologically-confirmed unresectable or metastatic GIST.
  - b. Have progressed on or are intolerant to imatinib therapy and have also received at least 1 of the following: sunitinib, regorafenib, ripretinib, or avapritinib.
3. For Expansion Phase Cohorts (Phase 2):
  - a. Cohort 1:
    - i. Have histologically- or cytologically confirmed unresectable or metastatic GIST.
    - ii. Have progressed on or are intolerant to imatinib, sunitinib, regorafenib and ripretinib.
  - b. Cohort 2:
    - i. Have histologically- or cytologically confirmed unresectable or metastatic GIST.
    - ii. Have progressed on or are intolerant to imatinib and sunitinib. Patients in this cohort are allowed to have received up to 1 additional line of therapy in the advanced/metastatic setting.

- c. Cohort 3:
  - i. Have histologically- or cytologically confirmed unresectable or metastatic GIST.
  - ii. Have progressed on or are intolerant to imatinib (including in the adjuvant setting).
  - iii. Have not received additional systemic therapy for advanced GIST.
4. Have at least 1 measurable lesion as defined by modified RECIST 1.1 ([Appendix 1](#)).
5. Have archival or new tumor biopsy tissue available to submit for mutational testing. A tumor sample obtained after most recent prior systemic anticancer therapy is preferred. Patients without appropriate archival tissue available may be discussed with the study medical monitor and approved for enrollment on a case-by-case basis.
6. Have Eastern Cooperative Oncology Group (ECOG) performance status (PS) of 0-2 ([Appendix 2](#)).
7. Adequate renal and hepatic function as defined by the following criteria:
  - a. Total serum bilirubin  $\leq 1.5 \times$  upper limit of normal (ULN) ( $< 3.0 \times$  ULN for patients with Gilbert syndrome),
  - b. Alanine aminotransferase (ALT) and aspartate aminotransferase (AST)  $\leq 3 \times$  ULN (or  $\leq 5 \times$  ULN if liver function abnormalities are due to underlying malignancy), and
  - c. Estimated (using Cockcroft-Gault formula or using the method standard for the institution) or measured creatinine clearance  $\geq 60$  mL/min.
8. Adequate bone marrow function as defined by the following criteria:

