## 4. PATIENT ELIGIBILITY

### 4.1 Inclusion Criteria

Patients must meet the following criteria to be eligible for participation in the study:

1. Male or female patient  $\geq$  18 years of age.
2. For Dose Escalation Phase Cohorts (Phase 1):
  - a. Have histologically- or cytologically-confirmed unresectable or metastatic GIST.
  - b. Have progressed on or are intolerant to imatinib therapy and have also received at least 1 of the following: sunitinib, regorafenib, ripretinib, or avapritinib.
3. For Expansion Phase Cohorts (Phase 2):
  - a. Cohort 1:
    - i. Have histologically- or cytologically confirmed unresectable or metastatic GIST.
    - ii. Have progressed on or are intolerant to imatinib, sunitinib, regorafenib and ripretinib.
  - b. Cohort 2:
    - i. Have histologically- or cytologically confirmed unresectable or metastatic GIST.
    - ii. Have progressed on or are intolerant to imatinib and sunitinib. Patients in this cohort are allowed to have received up to 1 additional line of therapy in the advanced/metastatic setting.
  - c. Cohort 3:
    - i. Have histologically- or cytologically confirmed unresectable or metastatic GIST.
    - ii. Have progressed on or are intolerant to imatinib (including in the adjuvant setting).
    - iii. Have not received additional systemic therapy for advanced GIST.
4. Have at least 1 measurable lesion as defined by modified Response Evaluation Criteria in Solid Tumors (RECIST) 1.1 ([Appendix 1](#)).

5. Have archival or new tumor biopsy tissue available to submit for mutational testing. A tumor sample obtained after most recent prior systemic anticancer therapy is preferred. Patients without appropriate archival tissue available may be discussed with the study medical monitor and approved for enrollment on a case-by-case basis.
6. Have Eastern Cooperative Oncology Group (ECOG) performance status (PS) of 0-2 ([Appendix 2](#)).
7. Adequate renal and hepatic function as defined by the following criteria:
  - a. Total serum bilirubin  $\leq 1.5 \times$  upper limit of normal (ULN) ( $< 3.0 \times$  ULN for patients with Gilbert syndrome),
  - b. Alanine aminotransferase (ALT) and aspartate aminotransferase (AST)  $\leq 3 \times$  ULN (or  $\leq 5 \times$  ULN if liver function abnormalities are due to underlying malignancy), and
  - c. Estimated (using Cockcroft-Gault formula or using the method standard for the institution) or measured creatinine clearance  $\geq 60$  mL/min.

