4.15.2 Laboratory Data

QMD Ref: CCI	Governing QMD: CCI
Confidentiality Statement	
CCI	

CCI		Sponsor: Theseus Pharmaceuticals, Inc.	
CCI		Protocol Number: THE630-21-101	
STATISTICAL ANALYSIS PLAN. PHASE 2-3-4			

Laboratory samples will be analyzed by local laboratories. For reporting purposes, lab parameters will be reported using SI units.

Each measurement (continuous data) will be classed as below, within, or above normal range, based on ranges supplied by the laboratory used. To identify laboratory values of potential clinical importance, National Cancer Institute Common Terminology Criteria for Adverse Events (CTCAE) will be used to assign grades for select laboratory parameters where applicable (See [Appendix 4](#)). A shift table representing two-way frequency tabulation for baseline and the worst post-baseline value according to the CTCAE grade, by cohort and overall, will be provided. For analysis purpose, patients with a lab parameter value that does not meet CTCAE criteria (e.g., value is within normal range) at baseline or any time post-baseline, will be assigned a Grade of 0 for said visit.

The incidence of patients meeting Hy’s law criteria will be summarized for any time, post-baseline (See [Appendix 5](#)).

A listing of any abnormal laboratory measurements recorded throughout the study will be presented.

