4.15.6 Electrocardiogram Data

The number (%) of patients meeting the following criteria at any time, post-baseline will be summarized by cohort and overall:

- QT interval (ms)
 - >500 & baseline \leq 500
- QTcF maximum increase (on treatment defined as any assessment on or after first dose up to last dose + 30 days)
 - No increase
 - >0 to <30 ms
 - 30 to 60 ms
 - >60 ms
- QTcF (ms)
 - >500 & baseline \leq 500
 - >480 & baseline \leq 480
 - >450 & baseline \leq 450
- Heart Rate (bpm)
 - <60 bpm
 - <50 bpm
 - >100 bpm
 - >100 bpm and 25% increase from baseline
 - < 50 bpm and 25% decrease from baseline

QMD Ref: CCI	Governing QMD: CCI
Confidentiality Statement	
CCI	

CCI			
CCI		Sponsor:	Theseus Pharmaceuticals, Inc.
		Protocol Number:	THE630-21-101
STATISTICAL ANALYSIS PLAN. PHASE 2-3-4			

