13 APPENDIX 5: CRITERIA BASED ON HY'S LAW

The following criteria for potential Hepatotoxicity are based on Hy's law. For criterion which requires multiple parameters to have a certain value (e.g., ALT>3x ULN and TBIL (total bilirubin)> 2xULN), all lab parameters values must be from samples with the same sample collection date.

ALT exceeds thresholds

- $\geq 3x$ ULN to $< 5x$ ULN
- $\geq 5x$ ULN to $< 8x$ ULN
- $\geq 8x$ ULN to $< 10x$ ULN
- $\geq 10x$ ULN

AST exceeds thresholds

- $\geq 3x$ ULN to $< 5x$ ULN
- $\geq 5x$ ULN to $< 8x$ ULN
- $\geq 8x$ ULN to $< 10x$ ULN
- $\geq 10x$ ULN

ALT or AST exceeds thresholds

- $\geq 3x$ ULN to $< 5x$ ULN
- $\geq 5x$ ULN to $< 8x$ ULN
- $\geq 8x$ ULN to $< 10x$ ULN
- $\geq 10x$ ULN

Other criteria

- Total Bilirubin (TBIL) $> 2x$ ULN
- ALP $> 1.5x$
- (ALT or AST $> 3x$ ULN) and (TBIL $> 2x$ ULN or INR > 1.5)*
- (ALT or AST $> 3x$ ULN) and TBIL $\geq 2x$ ULN and ALP $< 2x$ ULN*

*Criterion which requires multiple parameters to have a certain value (e.g., "and"), it is assumed that all lab parameter values are from the same sample.

QMD Ref: CCI	Governing QMD: CCI
Confidentiality Statement	
CCI	

80046695-study-11.01.01-20240109-sap_v3.0

Final Audit Report

2024-01-10

Created:	2024-01-09
By:	PPD
Status:	Signed
Transaction ID:	PPD

"80046695-study-11.01.01-20240109-sap_v3.0" History

-  Document created by PPD
2024-01-09 - 10:33:30 PM GMT
-  Document emailed to PPD) for signature
2024-01-09 - 10:34:24 PM GMT
-  Document emailed to PPD for signature
2024-01-09 - 10:34:25 PM GMT
-  Document emailed to PPD for signature
2024-01-09 - 10:34:25 PM GMT
-  PPD authenticated with Adobe Acrobat Sign.
2024-01-09 - 10:34:57 PM GMT
-  Document e-signed by PPD
Signing reason: I am the author of this document
Signature Date: 2024-01-09 - 10:34:58 PM GMT - Time Source: server
-  Email viewed by PPD
2024-01-09 - 10:50:46 PM GMT
-  PPD authenticated with Adobe Acrobat Sign.
Challenge: The user opened the agreement.
2024-01-09 - 10:51:02 PM GMT
-  PPD authenticated with Adobe Acrobat Sign.
2024-01-09 - 10:52:41 PM GMT
-  Document e-signed by PPD
Signing reason: I am the reviewer of this document
Signature Date: 2024-01-09 - 10:52:43 PM GMT - Time Source: server

 Email viewed by PPD

2024-01-10 - 2:16:46 PM GMT

 PPD authenticated with Adobe Acrobat Sign.

Challenge: The user completed the signing ceremony.

2024-01-10 - 2:17:35 PM GMT

 Document e-signed by PPD

Signing reason: I approve this document

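### The potential-hepatotoxicity table can count patients whose liver tests have not changed since entry, because its cut-offs ignore baseline

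*SAP*

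**What the plan says.** SAP 4.15.2 plans a summary in which Hy's "law criteria will be summarized for any time, post-baseline". It feeds Table 14.3.4.5 (potential hepatotoxicity) and Listing 14.3.4.6 (the flagged patients).

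Appendix 5 opens with "The following criteria for potential Hepatotoxicity are based on" Hy's law and then lists:
- ALT, AST, and ALT-or-AST tiers starting at 3x, 5x, 8x and 10x ULN;
- "Total Bilirubin (TBIL) $> 2x$ ULN";
- an ALP row above 1.5x;
- a first composite, "ALT or AST $> 3x$ ULN) and (TBIL $> 2x$ ULN or INR > 1.5";
- a second composite: ALT or AST above 3x ULN, bilirubin at least 2x ULN and ALP below 2x ULN.

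None of these refers to baseline or to anticoagulant use.

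Protocol 4.1, inclusion criterion 7, allows ALT and AST up to 3x ULN, rising to 5x "ULN if liver function abnormalities are due to underlying malignancy". Bilirubin may be up to 1.5x ULN, or below 3x ULN with Gilbert syndrome. Sections 4.1 and 4.2 set no limit on ALP or INR, and Protocol Table 7 does not exclude anticoagulants.

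**The concern.** The entry limits overlap the cut-offs, so a patient can meet a row before the first dose. If nothing changes on treatment, that patient is still tabulated as potential hepatotoxicity of a first-in-human drug. Pre-existing liver involvement, Gilbert syndrome or a therapeutic INR can then look like an on-treatment finding.

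The composites matter most. They are what a reader looks for under the name Hy's law, and Table 14.3.4.5 is their only planned summary. The single-parameter shift tables cannot show two abnormalities in the same sample. Under SAP 4.9, concomitant medications are neither summarized nor listed, so the outputs would not tell a reader whether an INR above 1.5 reflects anticoagulation.

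**Working it through.** The plan states no expected rate or precision for this table, so there is no figure to reproduce. The check compares entry limits with cut-offs and then applies the Appendix 5 rules to unchanged patients.

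**Step 1. Overlap of entry limits and cut-offs.**

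| Test | Entry limit (Protocol 4.1) | Appendix 5 cut-off | Eligible and already meeting it |
|---|---|---|---|
| ALT/AST | 3x ULN; 5x if malignancy | tiers from 3x ULN | exactly 3.0x; above 3.0x to 5.0x with malignancy |
| Bilirubin | 1.5x ULN; below 3x if Gilbert | above 2x ULN | above 2.0x to below 3.0x, Gilbert only |
| ALP | none | above 1.5x (reference not stated; ULN assumed) | any value above 1.5x |
| INR | none | above 1.5, within the first composite only | above 1.5, only with ALT or AST above 3x ULN |

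The tiers from 8x ULN upward cannot be met at entry. The tier from 5x can be met only at exactly 5.0x.

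**Step 2. Profiles with every post-baseline value equal to baseline.** Tests not named are normal.

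| Unchanged profile | Rows counted |
|---|---|
| ALT/AST 3.0x ULN | 3 to <5x tier |
| ALT/AST 4.0x ULN (malignancy) | 3 to <5x tier |
| ALT/AST 5.0x ULN (malignancy) | 5 to <8x tier |
| Bilirubin 2.5x ULN (Gilbert) | bilirubin |
| ALP 3x ULN | ALP |
| INR 2.5 on anticoagulation, normal ALT/AST | none |
| ALT 4x ULN with INR 2.5 | 3 to <5x tier; first composite |
| ALT 4x ULN with Gilbert bilirubin 2.5x and ALP below 2x ULN | 3 to <5x tier; bilirubin; both composites |

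Adding the condition that the criterion was not met at baseline removes every one of these counts.

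**Step 3. The same values under SAP Appendix 4.** When baseline is above ULN, ALT and AST Grade 1 starts at 1.5x baseline. Unchanged ALT of 4x ULN gives 4/4 = 1.0x baseline, hence Grade 0. Bilirubin Grade 1 requires more than 1.0x baseline. Unchanged 2.5x ULN gives 2.5/2.5 = 1.0, hence Grade 0. The chemistry shift table would show no change for patients whom Table 14.3.4.5 counts.

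**Step 4. Size of one such patient.** SAP section 1 gives 32 enrolled; all are assumed dosed.
- Overall: 1/32 = 3.1 points. For scale, the exact (Clopper-Pearson) 95% interval is 0 to 10.9% for 0/32 and 0.1 to 16.2% for 1/32. The SAP plans no interval for this table.
- Dose level of 3: 1/3 = 33.3 points. Dose level of 6: 1/6 = 16.7 points.
- With backfill (Protocol 5.3, up to 20 per dose level): 1/20 = 5.0 points, or 1/26 = 3.8 points if 20 are added to 6. The Full Analysis Set does not exclude backfill patients.

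**The case against.** Much of the separation is already available. The shift tables grade ALT, AST, bilirubin and ALP against an abnormal baseline, abnormal values are listed (14.3.4.1), and each flagged patient is listed (14.3.4.6). With 32 patients, case review is feasible. An any-time count also errs toward over-flagging and misses nobody. All of this stands for single parameters. It does not cover the composites, or an INR raised by medication.

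The SAP also has no uniform baseline rule. Section 4.15.6 summarizes patients "meeting the following criteria at any time, post-baseline will be summarized by cohort and overall"; its QT and QTcF cut-off rows require baseline at or below the cut-off, but its heart-rate rows below 60, below 50 and above 100 bpm do not. The QTcF rows are a useful model, not proof that Appendix 5 breaks a rule of the SAP.

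A reader might infer that therapeutic anticoagulation is itself counted as hepatotoxicity. It is not: INR enters only alongside ALT or AST above 3x ULN.

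A reader might also infer that the primary safety conclusion is compromised. The documents do not support this. DLTs are treatment-emergent events for which a relation to the drug cannot be ruled out (SAP 4.2.13.2), TEAEs require onset or worsening on treatment (SAP 4.15.1), and no DLT, MTD or RP2D rule uses Table 14.3.4.5.

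Finally, the table and listing shells are not in the documents, so baseline values may already be planned for Listing 14.3.4.6.

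**Conclusion.** The point holds as one about how a descriptive safety table reads. Appendix 5 can count unchanged patients as potential hepatotoxicity, and for the composites no other planned summary corrects this. A composite can be met at entry only when two things coincide: ALT or AST above 3x ULN under the malignancy exception, and either Gilbert-range bilirubin or, for the first composite, INR above 1.5. For ALT, AST and bilirubin singly, the overlap comes through the malignancy and Gilbert exceptions, apart from ALT or AST at exactly 3.0x ULN.

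The documents do not say how many of the 32 patients entered above a cut-off, so a claim that the table is materially inflated would go too far. The per-patient sizes above assume that all 32 were dosed and, for dose levels, the sizes shown. The change is worth making because it is cheap and the data are already collected.

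**What to change.** Keep all any-time rows in Table 14.3.4.5, so that no case is hidden, and amend SAP 4.15.2 and Appendix 5 to add:

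- **(a) ALT, AST and ALT-or-AST:** a cross-tabulation of baseline tier by worst post-baseline tier, with treatment-emergent meaning a higher tier than at baseline. A plain rule of met afterward and not met before would misfire on bounded tiers: a fall from 5.0x to 4x ULN would count as new in the 3 to <5x tier. A rise within a tier, such as 3.1x to 4.9x ULN, would still not count here, but 4.9/3.1 = 1.58x baseline is Grade 1 in the shift table.
- **(b) Bilirubin, ALP and the two composites:** a row for criterion met post-baseline and not met at baseline.
- **(c) First composite:** a split showing whether it was met through bilirubin or only through INR. Flag patients on medication coded B01A, as Appendix 4 already does for INR grading. Do not remove them, because that would hide genuine INR rises.
- **(d) Listing 14.3.4.6:** baseline ALT, AST, bilirubin, ALP and INR, if the shell does not already show them.

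Screening already collects chemistry and coagulation (Protocol 6.2), and SAP 4.2.2 already defines baseline. The cost is SAP wording, some programming and a longer table; no new data are needed.

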4.15.3 Vital Signs

To identify vital signs values of potential clinical importance, the following criteria will be used for the following vital signs parameters: systolic blood pressure (SBP) and diastolic blood pressure (DBP).

Parameter	Category (levels)
SBP (mmHg)	<120 mmHg 120-139 mmHg 140-159 mmHg ≥ 160 mmHg
DBP (mmHg)	<80 mmHg 80-89 mmHg 90-99 mmHg ≥ 100 mmHg

For systolic and diastolic blood pressure, a shift table representing two-way frequency tabulation for baseline and the maximum post-baseline value according to the above criteria, by cohort and overall, will be provided along with summary of any increases in category level.

QMD Ref: CCI	Governing QMD: CCI
Confidentiality Statement	
CCI	

CCI			
CCI	Sponsor:		Theseus Pharmaceuticals, Inc.
	Protocol Number:		THE630-21-101
STATISTICAL ANALYSIS PLAN. PHASE 2-3-4			

4.15.4 Echocardiogram/MUGA

Standard continuous and categorical summaries will be presented for each visit by cohort and overall for the following parameters:

- Test type
- Left ventricular ejection
- Fraction (LVEF) % value (observed; change from baseline)
- If LVEF was clinically significant

4.15.5 ECOG Performance Status

Baseline ECOG performance status scale scores will be summarized by cohort and overall (Section 4.8).

4.15.6 Electrocardiogram Data

The number (%) of patients meeting the following criteria at any time, post-baseline will be summarized by cohort and overall:

- QT interval (ms)
 - >500 & baseline \leq 500
- QTcF maximum increase (on treatment defined as any assessment on or after first dose up to last dose + 30 days)
 - No increase
 - >0 to <30 ms
 - 30 to 60 ms
 - >60 ms
- QTcF (ms)
 - >500 & baseline \leq 500
 - >480 & baseline \leq 480
 - >450 & baseline \leq 450
- Heart Rate (bpm)
 - <60 bpm
 - <50 bpm
 - >100 bpm
 - >100 bpm and 25% increase from baseline
 - < 50 bpm and 25% decrease from baseline

QMD Ref: CCI	Governing QMD: CCI
Confidentiality Statement	
CCI	

CCI			
CCI		Sponsor:	Theseus Pharmaceuticals, Inc.
		Protocol Number:	THE630-21-101
STATISTICAL ANALYSIS PLAN. PHASE 2-3-4			

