**Exclusion Criteria:**

Patients meeting any of the following criteria will not be eligible for participation in the study:

1. Received systemic anticancer therapy (including cytotoxic chemotherapy, investigational agent, antineoplastic monoclonal antibodies, or immunotherapy) less than 5 half-lives or 14 days (whichever is shorter) prior to the first dose of study drug.
2. Patients known to be both KIT and PDGFRA wild-type.
3. Received radiotherapy within 14 days prior to the first dose of study drug.
4. Major surgical procedure within 28 days of the first dose of study drug. Minor surgical procedures such as central venous catheter placement or minimally invasive biopsy are allowed.
5. Have known untreated or active central nervous system metastases.
6. 12-lead electrocardiogram (ECG) demonstrating QT interval corrected by Fridericia's formula (QTcF) > 470 msec at screening, or history of long QTc syndrome.
7. Have significant, uncontrolled, or active cardiovascular disease, including, but not restricted to:
  - a. Myocardial infarction (MI) within 6 months prior to the first dose of study drug
  - b. Unstable angina within 6 months prior to first dose of study drug
  - c. Symptomatic congestive heart failure (New York Heart Association classes II-IV) ([Appendix 4](#)) within 6 months prior to first dose of study drug
  - d. Clinically significant, uncontrolled atrial arrhythmia (as determined by the Investigator)
  - e. Any history of ventricular arrhythmia
  - f. Cerebrovascular accident or transient ischemic attack within 6 months prior to first dose of study drug
  - g. Uncontrolled hypertension at study entry. Patients with hypertension should be under treatment on study entry to control blood pressure.
8. Have an active uncontrolled infection, including, but not limited to, the requirement for intravenous antibiotics.
9. Patients with a known allergy or hypersensitivity to any component of the study drug. Patients with a history of Stevens-Johnson syndrome on a prior tyrosine kinase inhibitor (TKI) are excluded.
10. Any active bleeding excluding hemorrhoidal or gum bleeding.

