### 9.6.2 QTcF Analysis

Descriptive statistics of maximum QTcF and change from baseline will be calculated following the ICH-E14 guidelines: the proportion of treated patients with at least 1 on-drug QTcF value >450 ms, 480 ms, and 500 ms; and the proportion of treated patients with a maximum change in QTcF from baseline >30 ms and >60 ms. The Fridericia correction (QTcF) will be used throughout. The association between QTcF changes and plasma levels of THE-630 will be analyzed using mixed effects models.

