7 CHANGES TO PLANNED PROTOCOL ANALYSIS

Due to the termination of this study, the scope of reporting has changed. This amendment documents the analyses to be performed, which are generally consistent with the protocol, but reflects the reduction in the scope of reporting.

QMD Ref: CCI	Governing QMD: CCI
Confidentiality Statement	
CCI	

	CCI		
	CCI	Sponsor:	Theseus Pharmaceuticals, Inc.
		Protocol Number:	THE630-21-101
STATISTICAL ANALYSIS PLAN. PHASE 2-3-4			

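### SAP 4.15.6 counts QTcF above 450 ms only in patients who start at or below 450 ms, so the protocol's unconditional proportion is not produced; its 30 ms band boundary also differs from the protocol's

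*SAP*

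**What the plan says.** Protocol 9.6.2, repeated in the synopsis under QTc Analysis, defines two sets of descriptive proportions. The first is "the proportion of treated patients with at least 1 on-drug QTcF value >450 ms, 480 ms, and 500 ms". The second is "the proportion of treated patients with a maximum change in QTcF from baseline >30 ms and >60 ms". Neither carries a condition on the baseline value.

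SAP 4.15.6 attaches a baseline condition to every absolute cut-off. The rows are ">450 & baseline" at or below 450 ms, ">480 & baseline" at or below 480 ms and ">500 & baseline" at or below 500 ms. It bands the maximum QTcF increase as none, above 0 to below 30 ms, 30 to 60 ms, and above 60 ms. These feed Table 14.3.7.2, the only ECG display in the SAP's list of tables, figures and listings.

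Exclusion criterion 6 removes patients with QTcF "> 470 msec at screening, or history of long QTc syndrome". SAP 4.2.2 takes baseline as the last value before the first dose, which need not be the screening ECG.

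On departures from the protocol, SAP Section 7 says: "This amendment documents the analyses to be performed, which are generally consistent with the protocol". It mentions a reduced scope and nothing about QTcF.

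**The concern.** The two documents describe different numerators under the same cut-offs. The protocol's quantity is how many treated patients were ever above the limit on drug. The SAP's quantity is how many newly crossed it. The entry limit of 470 ms lies above the lowest cut-off of 450 ms, so the trial can enrol patients who meet the protocol's criterion and can never meet the SAP's.

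Safety is the Phase 1 primary endpoint and Phase 2 will not open, so these 32 patients provide all the QTc data this trial will report. A reader who expects the protocol's proportion above 450 ms would be given a number that can be lower than it and cannot be higher.

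The band boundary is a second, smaller mismatch. It works in the opposite direction.

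**Working it through.** The documents give no QTcF result or planning figure to reproduce. The check compares the two rules directly.

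**Inputs**
- Protocol rules: Protocol 9.6.2.
- SAP rules: SAP 4.15.6.
- Screening limit of 470 ms: exclusion criterion 6.
- Baseline as last pre-dose value: SAP 4.2.2.
- Triplicate means rounded to whole milliseconds: SAP 4.2.13.1. A rise of exactly 30 ms can therefore occur.
- 32 patients enrolled, Phase 1 only: SAP Section 1.

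**Rules.** Let b be baseline, m the post-baseline maximum, d = m − b, and c a cut-off.
- Absolute value. Protocol: m > c. SAP: m > c and b ≤ c. They differ exactly when m > c and b > c.
- Change above 30 ms. Protocol: d > 30. SAP, adding the 30 to 60 and above-60 bands: d ≥ 30. They differ exactly when d = 30.
- Change above 60 ms. Both: d > 60. No difference.

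**Enumeration.** Both rules were applied to every whole-millisecond pair with m from 380 to 560. Baseline ran from 380 to 470 (the range if baseline stays within the screening limit), then from 380 to 510 (allowing a rise between screening and first dose).

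| Criterion | Pairs that differ, b ≤ 470 | Pairs that differ, b ≤ 510 | Direction |
|---|---|---|---|
| above 450 ms | 20 × 110 = 2,200 (b 451–470) | 60 × 110 = 6,600 (b 451–510) | SAP omits |
| above 480 ms | 0 | 30 × 80 = 2,400 (b 481–510) | SAP omits |
| above 500 ms | 0 | 10 × 60 = 600 (b 501–510) | SAP omits |
| rise above 30 ms | 91 (all d = 30) | 131 (all d = 30) | SAP adds |
| rise above 60 ms | 0 | 0 | none |

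The pair counts show where the rules part, not how often patients fall there. For the 480 or 500 ms row to differ, QTcF must rise by at least 481 − 470 = 11 ms or 501 − 470 = 31 ms between screening and the last pre-dose reading.

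**Two patients**
- Baseline 455, maximum 479 ms. The protocol counts this patient as above 450. The SAP puts the patient in no threshold row, only in the band above 0 to below 30 ms (rise 24).
- Baseline 465, maximum 495 ms. The protocol counts above 450 and above 480, but not a rise above 30. The SAP counts above 480 and the 30 to 60 ms band, but not above 450.

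**Size.** Each omitted patient moves the overall proportion by 1/32 = 3.1 percentage points. Within a dose level, one patient is 1/6 = 16.7 points in a cohort of six. As an illustration with assumed counts, suppose 6 of 32 patients have any on-drug QTcF above 450 ms, and k of them began above 450 ms:

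| k | Protocol | SAP, denominator 32 |
|---|---|---|
| 0 | 6/32 = 18.8% | 6/32 = 18.8% |
| 1 | 18.8% | 5/32 = 15.6% |
| 2 | 18.8% | 4/32 = 12.5% |
| 3 | 18.8% | 3/32 = 9.4% |

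If k = 3, and no other patient began above 450 ms, an at-risk denominator would give 3/29 = 10.3%. That is a proper treatment-emergent rate, but still not the protocol's quantity.

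**Can the protocol figure be recovered elsewhere?** SAP 4.2.13.3 and 4.3 speak of listing the data. However, the version 3.0 entry in the SAP history drops ECG descriptive summaries and all listings except those numbered as tables, and the listing section for other safety data is empty. No planned display shows how many patients had a baseline above 450 ms.

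**The case against.** A baseline-conditioned count is a legitimate treatment-emergent summary: a patient at 455 ms before dosing who stays above 450 ms has not newly crossed the limit, and any rise still appears in the increase bands. Protocol 9.1 leaves the definition of analysis variables to the SAP. The output is descriptive, enrolment stopped at 32, and the practical effect may be a handful of patients in one row, or none. SAP version 1.0, which the current version cites for its details, is not available here and may explain the criteria.

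Much of this stands as a limit on importance. It does not remove the mismatch. The protocol names a specific proportion, the SAP replaces it rather than adding to it, and the current Section 7 does not say so. The SAP's own practice elsewhere also favours showing both views: heart rate in 4.15.6 has rows with and without a baseline condition, and blood pressure in 4.15.3 gets a baseline-to-maximum shift table.

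A reader might infer more than the documents support:
- That all three threshold rows fail. With baseline at or below 470 ms, the 480 and 500 ms conditions remove nobody.
- That the table understates QTc effects throughout. The 30 ms boundary raises the count, and the above-60 band is unaffected.
- That the affected figure is the main QTc result. Protocol 9.6.2 lists five proportions and ranks none.
- That the percentages are certainly of all patients. SAP 4.15.6 states no denominator. The 4.3 default of non-missing observations points that way, but the table shells are not in the documents.

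**Conclusion.** The point holds for the proportion above 450 ms. As written, the SAP does not produce the protocol's figure, can only understate it, and leaves no other planned output from which to rebuild it. The understatement is 3.1 percentage points for each patient who has both a baseline and an on-drug QTcF above 450 ms. This assumes that all 32 enrolled patients were dosed and have the needed ECGs, and that the 4.3 default denominator applies.

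The number of such patients is unknown. The documents give no QTcF mean or spread. Fitting an assumed distribution truncated at 470 ms would also model the screening value rather than the SAP's pre-dose baseline, so no expected count is offered.

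The 480 and 500 ms rows share the form but depart from the protocol only if the pre-dose reading rose above those cut-offs after screening. The 30 ms boundary is a separate, minor error that overcounts only rises of exactly 30 ms. The change is worth making because the protocol's quantity is explicit and the remedy is nearly free, not because a large distortion has been shown.

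**What to change.** In Table 14.3.7.2 and SAP 4.15.6:

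1. Add rows for any on-treatment QTcF above 450 ms regardless of baseline and, for consistency, above 480 and above 500 ms. A baseline-by-maximum shift table would serve equally well. State the time window for these rows: the SAP currently defines on-treatment (first dose to last dose plus 30 days) only for the increase item and takes the absolute categories at any post-baseline time.
2. Keep the conditional rows, label them treatment-emergent, and give their denominator as patients with baseline at or below the cut-off.
3. Change the increase bands to above 0 to 30, above 30 to 60, and above 60 ms.
4. Record the added treatment-emergent definition in SAP Section 7.

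The cost is a few extra rows in one table, from data already collected. The reported proportion above 450 ms may come out higher.
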